5. STUDY ENROLLMENT AND WITHDRAWAL

5.1. Inclusion Criteria

To be included in the study, subjects with acne vulgaris must meet the following inclusion criteria.

1. Subject (or legal guardian) has the ability and willingness to sign a written informed consent/assent.
2. Subject is of either gender and 12 to 40 years of age.
3. Subject is in good general health without clinically significant haematological, cardiac, respiratory, renal, endocrine, gastrointestinal, psychiatric, hepatic, or malignant disease, as determined by the investigator.
4. Subject has suitable venous access for blood sampling.
5. Subject is able and willing to complete the study and to comply with all study instructions and attend the necessary visits.
6. Subject has acne vulgaris of the face defined as:
 - a. 20 to 50 (inclusive) inflammatory lesions on the face
 - b. 20 to 100 (inclusive) non-inflammatory lesions on the face
 - c. An Investigator's Global Assessment (IGA) score for acne severity of 3 or 4 (moderate or severe) assessed on the face.
7. Subject has ≤ 2 nodular/cystic acne lesions (>5 mm in diameter).
8. Subject must refrain from the use of other treatments for acne during the study.
9. Subject must agree to not wash or shave their face, swim or otherwise get their face wet for at least 1 hour after application of study medication.
10. Subject must agree to maintain their regular use of sunscreens, moisturizers, shaving cream, and facial make up throughout the entire course of the study.
11. Male subjects and their partners must agree and commit to use a barrier method of contraception during the study and for 90 days after last study drug application.
12. A negative UPT result for all WOCBP at the Screening Visit and Baseline Visit, if applicable. A WOCBP is one who is not permanently sterilized or is not postmenopausal. Postmenopausal is defined as 24 months with no menses without an alternative medical cause.

13. Sexually active women must agree to use the following throughout the study and for 30 days after last study drug application:
 - a. One of these highly effective contraception methods
 - i. Intrauterine device (IUD); hormonal (injections, implants, transdermal patch, vaginal ring; tubal ligation; partner vasectomy, OR
 - b. Oral contraceptives WITH a barrier method (listed below), OR
 - c. Two barrier forms of contraception (listed below)
 - i. Male or female condom; diaphragm; cervical cap.
14. Male subjects must refrain from sperm donation during the study treatment period until 90 days after final study drug administration.
15. Male subjects must agree to keep their face clean shaven (no moustache or goatee; short sideburns acceptable) throughout the study and use the same method for shaving as was used for the 4 weeks prior to the Screening Visit.

5.2. Exclusion Criteria

If a subject meets any of the following exclusion criteria, they may not participate in the study.

1. People who would otherwise qualify for the study but are living in the same household as a study subject, are not allowed to participate in the study.
2. Female subject who is breast feeding, pregnant, or planning to become pregnant any time during the course of the study.
3. Subject with history of known or suspected intolerance to the drug product excipients.
4. Subject has known HIV infection.
5. Subject has acne conglobata, acne fulminans, secondary acne (chloracne), pseudo-folliculitis, severe acne requiring systemic treatment, or is taking a medication known to induce or exacerbate acne.
6. Subject has severe truncal acne.
7. Subject has excessive facial hair that would interfere with the evaluation of safety or with the diagnosis or assessment of acne vulgaris.
8. Subject has sunburns, unevenness in skin tones, tattoos, scars, excessive hair, freckles, birthmarks, moles, or other skin damage or abnormality that would result in the inability to evaluate the skin of the face.
9. Subject has any skin condition of the face other than acne vulgaris.
10. Subject has used oral retinoid (e.g. isotretinoin) within 6 months (180 days) prior to the Baseline Visit.

11. Subject has used Vitamin A supplements greater than 10,000 units/day within 6 months (180 days) prior to the Baseline Visit.
12. Subject has used androgen receptor blockers (such as spironolactone or flutamide) within 3 months (90 days) prior to the Baseline Visit.
13. Subject has initiated treatment with hormonal therapy or changed dosing with hormonal therapy within 3 months (90 days) prior to the Baseline Visit. Note: Dose and frequency of any hormonal therapy started more than 3 months (90 days) prior to the Baseline Visit must remain unchanged throughout the study. Hormonal therapies include, but are not limited to, anabolic steroids and birth control pills. Subjects taking testosterone therapy are excluded from participation.
14. Subject has had facial procedures (chemical or laser peel, microdermabrasion, etc.) within 8 weeks (56 days) prior to the Baseline Visit.
15. Subject has had treatment with systemic antibiotics within 4 weeks (28 days) prior to the Baseline Visit.
16. Subject has had treatment with systemic anti-acne drugs within 4 weeks (28 days) prior to the Baseline Visit.
17. Subject has had treatment with systemic anti-inflammatory drugs within 4 weeks (28 days) prior to the Baseline Visit.

Note: Occasional non-steroidal anti-inflammatory drugs (NSAIDs) and aspirin use on an as-needed basis, and if not used consecutively for >14 days prior to the Baseline Visit, is acceptable and does not require washout. Subjects receiving intranasal and inhaled corticosteroids may participate. Low dose (81mg) aspirin taken daily is acceptable.
18. Subject has had treatment with systemic (oral) corticosteroids other immunosuppressive medications within 4 weeks (28 days) prior to the Baseline Visit.
19. Subject has had treatment with prescription topical retinoid use on the face (e.g. tretinoin, tazarotene) within 4 weeks (28 days) prior to the Baseline Visit.
20. Subject has had treatment with topical prescription antibiotics (e.g. dapsone, clindamycin, erythromycin, or sulfacetamide) or combination products that include a topical antibiotic within 2 weeks (14 days) prior to the Baseline Visit.
21. Subject has had treatment with over-the-counter (OTC) topical medications for the treatment of acne vulgaris including benzoyl peroxide, topical anti-inflammatory medications, corticosteroids, adapalene, α -hydroxy/glycolic acid on the face within 2 weeks (14 days) prior to the Baseline Visit.
22. Subject is currently using any medication that, in the opinion of the investigator, may affect the evaluation of the study product or place the subject at undue risk.
23. Subject has had photodynamic therapy within 8 weeks (56 days) prior to the Baseline Visit.

24. Subject has used a tanning bed within 2 weeks (14 days) prior to the Baseline Visit.
25. Subject has used home-based light treatment within 2 weeks (14 days) prior to the Baseline Visit.

NOTE: Use of the treatments listed in Exclusion Criteria 10 through 25 above are not permitted throughout the study.

26. Subject has an underlying disease that requires the use of interfering topical or systemic therapy.
27. Subject has other dermatological conditions that require the use of interfering topical or systemic therapy or that might interfere with study assessments such as, but not limited to, atopic dermatitis, psoriasis, perioral dermatitis, or rosacea.
28. Subject has had excessive sun exposure (in the opinion of the investigator) within one week prior to the Baseline Visit and an unwillingness to refrain from excessive sun exposure during the study.
29. Subject has a clinically relevant history or currently suffering from any disease or condition that, in the opinion of the investigator, may affect the evaluation of the study product or place the subject at undue risk. This may include respiratory (including chronic asthma requiring repetitive drug interventions), gastrointestinal, renal, hepatic, hematological, lymphatic, neurological, cardiovascular, psychiatric, musculoskeletal, genitourinary, immunological, dermatological, or connective tissue diseases or disorders.
30. Subject has a clinically relevant history of, or current evidence of, abuse of alcohol or other drugs. Subjects may be deemed eligible if the UDS identifies subject-reported, prescribed drugs or appropriate levels of alcohol, as determined by the investigator.
31. Subject has participated in another investigational drug or device research study within 4 weeks (28 days) of the Baseline Visit or five half-lives of the drug, whichever is longer.
32. Any other reason that would make the subject, in the opinion of the investigator or sponsor, unsuitable for the study.

5.3. Subject Withdrawal or Termination

5.3.1. Reasons for Withdrawal or Termination

If a subject is withdrawn from the study, the subject's enrollment in the study will terminate and study drug application will be discontinued. Efforts will be made to perform all assessments scheduled for the Day 84 Visit prior to subject withdrawal. The Day 84 Visit should be scheduled for day 84 (± 5 days), if possible.

A subject may be withdrawn from further study participation under the following circumstances:

- At the subject's request.

- Noncompliance with protocol by the subject as determined by the study site staff and investigator.
- Adverse Event (decision to be removed from study made by either the investigator or subject). The investigator must notify the sponsor immediately if a subject is withdrawn because of an AE.
- Pregnancy.
- Decision by the investigator or sponsor that termination is in the subject's best medical interest or for an administrative decision for a reason other than that of an AE.
- Lost to follow-up, as determined by failure to respond to at least 2 telephone calls followed by certified letter sent to the subject's last known address. All attempts to contact the subject must be documented in the subject's source documents.
- Sponsor decision to halt the entire study.

5.3.2. Premature Termination or Suspension of Study

This study may be suspended or prematurely terminated if there is sufficient reasonable cause. Written notification, documenting the reason for study suspension or termination, will be provided by the suspending or terminating party to the investigator. If the study is prematurely terminated or suspended by the sponsor, the PI will promptly inform the Institutional Review Board (IRB) or Ethics Committee (EC) and will provide the reason(s) for the termination or suspension.

Circumstances that may warrant termination or suspension include, but are not limited to:

- Determination of unexpected, significant, or unacceptable risk to subjects,
- Insufficient compliance to protocol requirements,
- Data that are not sufficiently complete and/or evaluable.

The study may resume once concerns about safety, protocol compliance, or data quality are addressed and satisfy the sponsor and IRB/EC.

6. STUDY DRUG

6.1. Study Drug

6.1.1. Acquisition

Study drug will be provided to the US study sites by The Coghlan Group (TCG) in Bastrop, Texas, USA and to the Australian sites by Pharmaceutical Packaging Professionals (PPP) in Port Melbourne, Victoria, Australia. Initial shipments will be made to supply the study sites prior to enrollment of the first subject. Additional supplies will be made available as needed based on subject enrollment.

6.1.2. Formulations, Appearance, Packaging, and Labeling

Botanix Pharmaceuticals' BTX 1503 contains the active pharmaceutical ingredient, cannabidiol (CBD). CBD is a member of a broader family of compounds known as cannabinoids, a class of compounds originally derived from the *cannabis sativa* plant.¹ CBD is chemically synthesized under Good Manufacturing Practices (GMP) for use in this study.

The active study product is a clear to light yellow, slightly viscous liquid with a 2.5% or 5% (w/w) concentration of CBD in a formulation of excipients which have been used extensively in other topical products. The liquid spreads easily and quickly evaporates, leaving the CBD and a small amount of excipients on the skin. The Vehicle liquid is identical in appearance to the BTX 1503 liquid.

Each milliliter of the BTX 1503 5% liquid formulation contains 37.5 mg of CBD. Each milliliter of the BTX 1503 2.5% liquid formulation contains 18.75 mg of CBD. All subjects will apply 2.0 mL, 4 pump actuations, of BTX 1503 BID or QD or Vehicle BID or QD based on their randomized treatment group. Subjects will receive the following daily exposure to CBD.

- Subjects randomized to BTX 1503 5% BID will apply 150.0 mg of CBD daily,
- Subjects randomized to BTX 1503 5% QD will apply 75.0 mg of CBD daily,
- Subjects randomized to BTX 1503 2.5% QD will apply 37.5 mg of CBD daily.

Study drug will be supplied in 60 mL multi-dose, metered pumps delivering 0.5 mL per actuation. Each pump for BID dosing will contain approximately 39 mL of study drug and each pump for QD dosing will contain approximately 21 mL of study drug. This will provide dosing for 7 days for all subjects. Pumps for all groups will be labeled identically, except for kit number and bottle number, to maintain the blind.

Study drug will be pumped into the palm of one hand and applied to the face using fingertips of the other hand. Study drug will be applied to the entire face, regardless of location of acne lesions.

Study drug will be provided in kits. Each kit will contain adequate study drug for 4 weeks of daily applications (28 days). Prior to distribution, pumps will be weighed by clinical site staff and the weights recorded in the source documents and the eCRF. Each kit will contain 4 pumps, one for

each week of dosing. When a subject is enrolled, the site will access the IWRS to receive a kit number for the first 28 days of dosing based on the IWRS randomization. At the Day 28 and Day 56 Visits, the site will access the IWRS to obtain the kit number for the following 28 days of dosing. All distributed pumps will be returned by the subject at the Day 28, Day 56, and Day 84 Visits and weighed to monitor compliance and document doses delivered.

The study drug bottle may include the following information:

Caution: New Drug--Limited by Federal (or United States) law to investigational use only.

KEEP OUT OF REACH OF CHILDREN

Drug Ingredient: BTX 1503 or Vehicle

Directions: Use in accordance with study drug application instructions.

FOR TOPICAL APPLICATION ONLY.

Protocol # BTX.2018.001

Flammable. Store between 15-30°C.

Bottle #

Kit #

Sponsor: Botanix Pharmaceuticals Ltd

6.1.3. Product Storage and Stability

The study drug will be stored at a controlled room temperature of 15°C to 30°C and should not be refrigerated. Prior to dispensing to the subject, the study drug will be stored in a secured location with access only by authorized study personnel. Study drug has been tested to ensure that there is adequate stability for the duration of the study. Retest dates may be included on the carton labeling.

6.1.4. Preparation

No preparation of the study drug is required.

6.1.5. Dosing and Administration

Subjects will receive their initial application of study drug on Day 1 at the clinical sites administered by the clinical site staff. When the subject is ready for study drug application, a pump is selected from the assigned study kit. The clinical site staff will remove the cap and apply the first dose of the study drug to the subject's entire face. All subsequent applications will be completed by the subject. To ensure that the entire face is covered, the study drug should be applied in a consistent manner for each application.

Subjects will be instructed in how to apply study drug. After their first application in the clinic subjects will apply their study drug at home. Each application of study drug will occur at the approximately the same time in the morning with the second application (for BID dosing groups) approximately 8 to 12 hours later. Subjects will apply study drug at the clinical site during the Day 14, Day 28, Day 56 and Day 84 Visits (final dose). A diary will be maintained documenting

compliance with the self-administered applications. All study drug bottles (used and unused) will be returned to the clinical site on the Day 28, Day 56, and Day 84 Visits.

Study drug should not be applied to the eyes or mouth. Subjects are to thoroughly wash their hands after study drug application. The study drug must not be handled by a family member or caregiver for study drug application.

6.1.6. Starting Dose

The dose for all subjects will be 2.0 mL, 4 pump actuations, of study drug applied to the entire face. No escalation of dose will occur.

6.1.7. Dose Adjustments/Modifications/Delays

There are no pre-planned dose adjustments, modifications, or delays.

6.1.8. Duration of Therapy

Subjects will apply study drug for 84 days with a final application on Day 84. Subjects receiving BID dosing will apply 167 doses and subjects receiving QD dosing will apply 84 doses.

6.1.9. Tracking of Dose

All subjects will be required to maintain a diary documenting each application of study drug. The subject will record that they applied each study dose. Subjects will return the study drug bottles (used and unused) at each visit. The clinical site staff will review the diary and count used/unused bottles to ensure subject compliance with dosing.

6.2. Study Drug Accountability Procedures

At each study visit the clinical site will weigh each pump dispensed to the subject and returned from the subject to calculate the amount (grams) of study drug used. The investigator will keep a current and accurate inventory of all clinical supplies received. These records will be reviewed at each monitoring visit performed by the CRA per SOPs.

7. STUDY PROCEDURES AND SCHEDULE

7.1. Study Specific Procedures/Evaluations

At the Screening Visit (Visit 1), all subjects/legal guardians will review and sign an informed consent/assent form attesting to their knowledge of the study requirements, risks, and benefits. The following study specific procedures will occur for all subjects at the Screening Visit:

- Demographics, height, weight, and a medical history, including alcohol and tobacco use, will be obtained,
- A review of systems will be conducted by the principal investigator or designee,
- All WOCBP will have a UPT conducted. The test must be negative for the subject to be enrolled,
- A urine drug screen will be conducted to ensure that the subject is not taking drugs of abuse,
- A count of inflammatory and non-inflammatory lesions on the face and an IGA will be collected,
- The subjects will be queried for concomitant medications that they are currently taking. Concomitant medications include all prescribed and over the counter (OTC) medications and any supplements, and
- Eligibility criteria will be reviewed to determine if subjects may proceed to study enrollment.

If subjects are eligible upon screening, they may be enrolled into the study on the same day.

At various visits throughout the study, the following will occur for all subjects to monitor the safety of the study drug treatment:

- Blood draws will be conducted for CBC and chemistry analysis,
- Collection of urine will occur for a urinalysis,
- Cutaneous tolerability assessments will be conducted by the principal investigator or an appropriately trained designee. Cutaneous tolerability will be graded using the following scale: 0, None; 1, Slight; 2, Moderate; 3, Severe. Evaluation for, and grading of, the following will be done at each evaluation:
 - Erythema (investigator assessed),
 - Scaling (investigator assessed),
 - Dryness (investigator assessed),
 - Pruritus in last 24 hours (subject reported), and
 - Burning/Stinging in last 24 hours (subject reported).

The definition for each level of grading for each tolerability assessment is provided in [Table 1](#).

Table 1. Cutaneous Tolerability Assessments Scale for Acne Vulgaris

| Tolerability Assessment | Severity | | | |
|-------------------------------------|---------------------|----------------------------------------------------------------------------------------------------------|-----------------------------------------------------------------------------------|---------------------------------------------------------------------------------------|
| | None = 0 | Mild = 1 | Moderate = 2 | Severe = 3 |
| Erythema | No erythema | Slight pinkness present | Definite redness, easily recognized | Intense redness |
| Scaling | No scaling | Barely perceptible shedding, noticeable only on light scratching or rubbing | Obvious but no profuse shedding | Heavy scale production |
| Dryness | No dryness | Slight but definite roughness | Moderate roughness | Marked roughness |
| Pruritus (in last 24 hours) | No itching | Only aware of itching at times; only present when relaxing; not present when focused on other activities | Often aware of itching; annoying; sometimes disturbs sleep and daytime activities | Constant itching; distressing; frequent sleep disturbance; interferes with activities |
| Burning/Stinging (in last 24 hours) | No Burning/Stinging | Slight warm, tingling/stinging sensation; not really bothersome | Definite warm, tingling/stinging sensation that is somewhat bothersome | Hot, tingling/stinging sensation that has caused definite discomfort |

- Subjects will be queried to report any AEs that have occurred since the last visit.
- Subjects will be queried to report any new medications or changes in current medications.

For all subjects, assessment of compliance with study drug application will be conducted through collection of a study diary on which subjects will record their daily administration. Subjects will be required to bring all used and unused study drug to each visit where the study site will assess compliance. At each study visit the clinical site will weigh each pump dispensed to the subject and returned from the subject to calculate the amount (grams) of study drug used.

The following efficacy assessments will be performed at the Screening, Baseline, Day 14, Day 28, Day 56, and Day 84 Visits:

- Counting of inflammatory and non-inflammatory lesions of the face by the principal investigator (PI) or appropriately trained designee. Thorough, documented, training will be provided to the PI and/or designee in the method for identifying and counting lesions.
- Administration of the IGA by the PI or appropriately trained designee. The IGA will be graded based on the scale provided in [Table 2](#).

Table 2. Investigator’s Global Assessment Scale for Acne Vulgaris

| Grade | | Description |
|----------|--------------|----------------------------------------------------------------------------------------------------------------------------------------------------------------------------|
| 0 | Clear | No evidence of facial acne vulgaris |
| 1 | Almost Clear | Few non-inflammatory lesions (comedones) are present; a few non-inflamed papules (papules must be resolving and may be hyperpigmented, though not pink-red) may be present |
| 2 | Mild | Several to many non-inflammatory lesions (comedones) are present; a few inflammatory lesions (papules/pustules) are present; no nodulo-cystic lesions |
| 3 | Moderate | Many non-inflammatory (comedones) and inflammatory (papules/pustules) are present; there may or may not be one small nodulo-cystic lesion |
| 4 | Severe | Significant degree of inflammatory disease; papules/pustules are a predominant feature; a few nodulo-cystic lesions may be present; many comedones may be present. |

- Photographs of the subject’s face will be obtained at selected sites at the Baseline Visit and the Day 84 Visit. Details on the methods for photography are provided in the Photography Manual.
- At Baseline and at Day 84, the Acne-QoL will be administered.

- On Day 84, the subject will be asked to complete the Patient Reported Outcome (PRO) to assess the perception of their acne relative to their baseline. The subject will complete the assessment to answer the following question: “Compared to the beginning of treatment, my acne is?” with a response of “Much better”, “Slightly better”, “The same”, “Slightly Worse”, or “Much worse”.

For purposes of conducting IGA scoring, the following definitions will apply:

- Open comedo - a widely dilated follicle, plugged with sebum and keratin (blackhead)
- Closed comedo - a small, flesh-colored closed follicle, filled with sebum and firm to palpation
- Papule - a small solid, inflamed, elevated lesion less than 5 mm in diameter
- Pustule - a circumscribed, erythematous raised skin lesion containing white exudate or pus, less than 5 mm in diameter
- Nodule - an erythematous, raised, firm, deep-seated papule equal to or greater than 5 mm in diameter

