4.2. Study Endpoints

4.2.1. Primary Efficacy Endpoint

The primary endpoint for the study is the absolute change from Baseline in inflammatory lesion counts at Day 84.

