10.1.8. Quality Assurance and Quality Control

Each clinical site, CRO, and laboratory participating in this study will have SOPs for quality management that describe:

- How data will be evaluated for compliance with the protocol, ethical standards, regulatory compliance, and accuracy in relation to source documents.
- The documents to be reviewed (e.g., eCRFs, clinic notes, product accountability records, specimen tracking logs, questionnaires, audio or video recordings), who is responsible, and the frequency for reviews.
- Who will be responsible for addressing QA issues (e.g., correcting procedures that are not in compliance with protocol) and QC issues (e.g., correcting errors in data entry).
- Staff training methods and how such training will be tracked.
- If applicable, calibration exercises conducted prior to and during the study to train examiners and maintain acceptable intra-and inter-examiner agreement.

QC procedures will be implemented beginning with the data entry system and data QC checks that will be run on the database will be generated. Any missing data or data anomalies will be communicated to the site(s) for clarification/resolution.

Following written SOPs, the clinical study monitors will verify that the clinical trial is conducted, and data are generated, documented (recorded), and reported in compliance with the protocol, GCP, and the applicable regulatory requirements (e.g., Good Laboratory Practices (GLP), Good Manufacturing Practices (GMP)).

The investigational site will provide direct access to all trial related sites, source data/documents, and reports for monitoring and auditing by the sponsor, and inspection by local and regulatory authorities.

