6.1.4 Adjustments for Covariates

Baseline lesion count will be a covariate for the efficacy endpoints for acne lesion counts. No other covariates are planned to be used in the analyses for this study.

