xxxxxx	xxxx	xxxxxxxx	xxxx-xx-xx (xx) xxxx-xx-xx (xx) xxxx-xx-xx (xx)	xx xx xx	xxxxxxxx xxxxxxxxxxx xxxxxxx x xxxxxxx xxxxxxxx xxxxxxxxxxx xxxxxxx x xxxxxxx xxxxxxxx xxxxxxxxxxx xxxxxxx x xxxxxxx
xxxxxx	xxxx	xxxxxxxx	xxxx-xx-xx (xx) xxxx-xx-xx (xx)	xx xx	xxxxxxx xx xxx xxx

¹ Day is calculated as date - date of first dose for dates prior to first dose. Otherwise, day is calculated as date - date of first dose + 1 for dates on or after first dose.
 SOURCE: USERNAME\SPONSOR\PROJECT\JOBNAME (DATE, TIME)

Listing 16.2.6.1: Lesion Count Evaluations
 Treatment Group
 (Page xx of yy)

S: Subject	V: Visit			Change from Baseline	Percent Change from Baseline	Reason Not Done
A: Age/Sex	D: Date/Time	Lesion Category	Count			
E: Evaluable	E: Evaluator Initials					
S: xxxxxx	V: SCREENING	Inflammatory	xx			
A: xxxx	D: xxxx-xx-xxTxx:xx:xx	Non-Inflammatory	xx			
E: xxxxxxxx	E: xx	Total Lesions	xxx			
	V: BASELINE	Inflammatory	xx			
	D: xxxx-xx-xxTxx:xx:xx	Non-Inflammatory	xx			
	E: xx	Total Lesions	xxx			
	V: DAY 14	Inflammatory	xx	xx	xxx	
	D: xxxx-xx-xxTxx:xx:xx	Non-Inflammatory	xx	x	xxxx	
	E: xx	Total Lesions	xx	xx	xxxx	

SOURCE: USERNAME\SPONSOR\PROJECT\JOBNAME (DATE, TIME)

Listing 16.2.6.2: Investigator Global Assessment
 Treatment Group
 (Page xx of yy)

S: Subject	Visit	Date/Time	Result	Two Grade Reduction from Baseline	Two Grade Reduction from Baseline and Achieving Clear or Almost Clear	Evaluator Initials or Reason Not Done
S: xxxxxx A: xxxx E: xxxxxxxx	SCREENING	xxxx-xx-xxTxx:xx:xx	x x xxxxxxxx			xxx
	BASELINE	xxxx-xx-xxTxx:xx:xx	x x xxxxxxxx			xxx
	DAY 14	xxxx-xx-xxTxx:xx:xx	x x xxxxxxxx	xx	xx	xxx
	DAY 28	xxxx-xx-xxTxx:xx:xx	x x xxxxxxxx	xx	xx	xxx
	DAY 56	xxxx-xx-xxTxx:xx:xx	x x xxxxxxxx	xx	xx	xxx
	DAY 84	xxxx-xx-xxTxx:xx:xx	x x xxxxxxxx	xx	xx	xxx
S: xxxxxx A: xxxx E: xxxxxxxx	SCREENING	xxxx-xx-xxTxx:xx:xx	x x xxxxxxxx			xxx
	BASELINE	xxxx-xx-xxTxx:xx:xx	x x xxxxxxxx			xxx
	DAY 14	xxxx-xx-xxTxx:xx:xx	x x xxxxxxxx	xx	xx	xxx
	DAY 28	xxxx-xx-xxTxx:xx:xx	x x xxxxxxxx	xx	xx	xxx
	DAY 56	xxxx-xx-xxTxx:xx:xx	x x xxxxxxxx	xx	xx	xxx
	DAY 84	xxxx-xx-xxTxx:xx:xx	x x xxxxxxxx	xx	xx	xxx

SOURCE: USERNAME\SPONSOR\PROJECT\JOBNAME (DATE, TIME)

Listing 16.2.6.3: Patient Reported Outcome Assessment
 Treatment Group
 (Page x of xx)

Subject	Age/Sex	Evaluable	Date of Assessment	Compared to the beginning of treatment, my acne is:	Reason Not Done
XXXXXXXXXX	XXXX	XXXXXXXXXX	XXXX-XX-XX	XXXXX XXXXXXXXX	
XXXXXXXXXX	XXXX	XXXXXXXXXX	XXXX-XX-XX	XXXXXXXX XXXXXXXXX	

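### No rule keeps the same evaluator for a subject at Baseline and Day 84, so rater differences can add avoidable noise to the lesion-count change endpoints

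*Protocol*

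**What the plan says.** The primary endpoint is a within-subject difference in a manual count: "The primary endpoint for the study is the absolute change from Baseline in inflammatory lesion counts at Day 84" (Protocol 4.2.1).

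Protocol 7.1 sets out who measures it. Its list opens "The following efficacy assessments will be performed at the Screening, Baseline, Day 14, Day 28, Day 56, and Day 84 Visits", and the entries include "Counting of inflammatory and non-inflammatory lesions of the face by the principal investigator (PI) or appropriately trained designee" and "Administration of the IGA by the PI or appropriately trained designee". The visit-by-visit lists in Protocol 7.3 call for the counts and the IGA without naming an evaluator. No section of the protocol or SAP asks for the same evaluator within a subject.

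The documents do contain safeguards:

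- **Training.** Protocol 7.1: "Thorough, documented, training will be provided to the PI and/or designee in the method for identifying and counting lesions". No agreement threshold is given.
- **Calibration.** Protocol 10.1.8 lists, among the things site, CRO and laboratory SOPs describe, "If applicable, calibration exercises conducted prior to and during the study to train examiners and maintain acceptable intra-and inter-examiner agreement".
- **Traceability.** The SAP's lesion-count and IGA listings (16.2.6.1 and 16.2.6.2) carry a field for "Evaluator Initials". No planned analysis uses it.

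The SAP model for lesion counts has treatment and the Baseline count only. Section 6.1.4 adds: "No other covariates are planned to be used in the analyses for this study". Neither rater nor site is modelled.

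**The concern.** Suppose a rater habitually counts a few lesions more or fewer than a colleague. If that rater makes both counts, the offset drops out of Day 84 minus Baseline. If the rater changes, the difference between the two offsets stays in the change score. Eligible Baseline inflammatory counts run only from 20 to 50 (Protocol 5.1, criterion 6a), so a difference of a few lesions is not negligible for an individual subject.

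What is at stake is precision in the comparisons the trial exists to make. The results are meant to inform dose and sample size for Phase 3 (Protocol 9.4.8; SAP 6.1.8), so extra noise in the change score would also feed into later variance planning.

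**Working it through.** **The plan's own figure.** The allocation is consistent: 360 × 2/8 = 90, 360 × 1/8 = 45, and 3 × 90 + 2 × 45 = 360. No power, effect size or SD stands behind it. Protocol 9.5 and SAP section 7 rest the size on clinical considerations, so there is no stated power to reproduce.

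**Inputs from the documents.** The primary analysis combines the two vehicle groups (SAP 6.8.1), so each primary contrast is 90 active versus 90 vehicle.

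**Assumed inputs.** Same-rater SD of change SD0 = 12 lesions; between-rater SD s = 2, 3 or 5 lesions; share f of subjects whose Baseline and Day 84 raters differ; two-sided 5% test. Offsets are treated as additive.

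**Change score.** Var(change) = SD0² + 2·f·s². With f = 1 the inflation factors are:

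- s = 2: (144 + 8)/144 = 1.06
- s = 3: (144 + 18)/144 = 1.13
- s = 5: (144 + 50)/144 = 1.35

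The difference detectable with 80% power when every subject keeps one rater is 12 × √(2/90) × (1.960 + 0.842) = 5.01 lesions. Power for that same difference becomes:

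| Share switching | s = 2 | s = 3 | s = 5 |
|---|---|---|---|
| 25% | 79.5% | 78.8% | 76.7% |
| 50% | 78.9% | 77.6% | 73.4% |
| 100% | 77.8% | 75.2% | 67.5% |

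If all subjects switch, regaining 80% needs 95, 102 or 122 per group instead of 90. Varying SD0 from 10 to 15 as well, over the same s and f, power runs from 79.7% down to 62.8%.

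**Planned ANCOVA.** Let VB and V84 be the Baseline and Day 84 variances without rater error, and c their covariance. The residual variance is:

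- same rater: V84 + s² − (c + s²)²/(VB + s²)
- different raters: V84 + s² − c²/(VB + s²)

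Assume a Baseline SD of 8, a Day 84 SD of 12 and correlation 0.5, so c = 48. For s = 3:

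- same rater: 153 − 57²/73 = 108.5
- different raters: 153 − 48²/73 = 121.4
- ratio: 1.12

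For s = 2 and s = 5 the ratios are 1.05 and 1.31. With all subjects switching, power falls from 80% to 77.9%, 75.4% and 68.7% for s = 2, 3 and 5. At s = 3 the ratio is 1.06 for correlation 0.3 and 1.24 for correlation 0.7. Baseline adjustment therefore does not remove the problem.

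**IGA endpoints.** Entry requires a Baseline IGA of 3 or 4 (Protocol 5.1, criterion 6c). A Day 84 grade of 1 is then a fall of 3 − 1 = 2 or 4 − 1 = 3 grades, and grade 0 a larger one. For eligible subjects, reaching grade 0 or 1 and the composite success definition are the same event, decided by the Day 84 rating alone. The SAP's logistic model has treatment as its only factor, so the Baseline rating does not enter as a covariate either. Only the separate 2-grade-reduction endpoint can depend on the Baseline rating: a Day 84 grade of 2 counts as success if Baseline was 4 and as failure if it was 3.

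**The case against.** Allowing the investigator or a trained designee is coherent and contradicts nothing in the plan. Training in counting is promised and documented, the IGA has a graded scale with lesion definitions, and initials make any switch traceable. The training materials, SOPs and monitoring plan are not available here and may address evaluator continuity. The trial claims no power, calls its tests exploratory and says non-significance does not mean failure (Protocol 9.2). All of this stands. It limits how much the point matters, but it does not supply the missing rule.

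Three stronger readings are tempting, and the documents do not support them:

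- **Bias.** A reader might infer that the treatment comparison is biased. Site personnel are blinded (SAP 4.1.3) and randomization is by site (SAP 4.1.2), so rater error is expected to be unrelated to active versus vehicle.
- **All IGA success endpoints.** A reader might extend the problem to every IGA endpoint. The entry criterion rules that out for two of the three secondary ones, as shown above.
- **A loss measured against 360 subjects, or against 45 per vehicle arm.** The primary contrasts are 90 versus 90. Comparisons with a single 45-subject vehicle group are exploratory (SAP 6.8.3), and no planned test compares one dose directly with another.

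It is also fair to say that a same-evaluator rule removes only additive offsets. A rater who over-counts in proportion to the true number distorts the absolute change even when making both counts.

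**Conclusion.** The point holds as a minor, inexpensive improvement. The plan permits a change of evaluator between Baseline and Day 84, and neither the design nor the model removes the resulting variance from the primary endpoint, the other lesion-count change endpoints or the 2-grade-reduction IGA endpoint.

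The size cannot be determined from the documents. For a 90 versus 90 contrast starting at 80% power, the change-score illustration gives 78.9% to 67.5% when half to all subjects switch and the rater SD is 2 to 5 lesions, with SD of change 12. The lower end needs a 5-lesion rater SD despite training and a switch in every subject. With good agreement or rare switching the loss would be trivial.

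**What to change.** Add to Protocol 7.1 that the same evaluator performs a given subject's lesion counts and IGA at all visits wherever possible, and at minimum that the evaluator whose assessment serves as Baseline also performs Day 84. Any switch should be documented through the evaluator initials already planned for the listings.

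The cost is one protocol sentence and some scheduling effort at sites, within the existing visit windows (±5 days at Day 84). It needs no new staff and no new data field. Because the rule is qualified, some switches will still occur, but they will be exceptions on record.
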